## g. Instrumentation:

The Stryker Intra-compartmental pressure monitor will be used for the standard of care diagnosis of compartment syndrome.

## 4. HUMAN SUBJECT PROTECTION

## **Recruitment and Consent Processes:**

All patients referred to the sports medicine clinic for leg pain will be screened for possible inclusion into the study, following standard of care clinical tests. After an initial standard of care evaluation, if CECS is suspected, each subject will be tested for compartment syndrome using standard of care clinical tests. If they are diagnosed with CECS, they will be asked to participate in the study and will be formally consented by a member of the research team.

Other exertional causes of leg pain will be ruled out by a standard of care clinical examination (general, orthopedic, neurologic, and functional) and supporting workup. These tests will include plain radiographs of the knee, tibia, fibula, and ankle on the affected side of the lower extremity. Any patient with an abnormal finding not consistent with CECS, such as stress fracture, will be ruled out from participating in the research study. Patients will have tried conservative treatment for at least 2 months prior to compartment testing to include rest, stretching, ice, and NSAIDs. All patients reporting lower extremity pain will be examined by one of the study physicians to confirm CECS, under direct supervision of [name].

Consent Pro	Consent Processes:					
How will you		Will obtain concept	▼ Telephone	Submit Form F – HIPAA and Consent Waiver and Alteration Form.		
consent subjects to	X	Will obtain consent without a signature	Is the information collected for the study health information?	Yes, submit Form F – HIPAA and Consent Waiver and Alteration Form.		
participat e in the research?	Will exclude some of the required elements of consent in the consent form, information sheet, consent process		e required elements of form, information sheet, or	Submit Form F – HIPAA and Consent Waiver and Alteration Form.		

Prospective Subjects: Informed Consent and HIPAA Authorization will be sought in advance from each prospective subject and appropriately documented in accordance with 32 CFR 219.117. Potential subjects will be notified about the study either through posted advertisements or by their primary care provider. Investigators will provide a written copy of the Informed Consent (ICD) and HIPAA Authorization (HIPAA) to the subject. The subject may decline to participate without prejudice. At the subject's discretion, they may take the ICD and HIPAA home to discuss further prior to making a decision. If the subject consents, a copy of the ICD and HIPAA will be given to them. No vulnerable populations are included in this research study. Subjects who cannot provide ICD and HIPAA will not be allowed to patriciate. No Legally Authorized Representatives will be utilized. Some patients may be patients of the PI or AI, however, they will have the study staff recruit their patients to prevent any misconception of coercion or undue influence.

Retrospective Subjects: Each subject will be verbally consented over the phone using the Telephone Consent prior to being asked any questions. The subject may decline to participate without prejudice. An approved HIPAA waiver is being utilized.

Recruiting Service	Will you be recruiting service members in a group setting?		~
Members	will you be recruiting service members in a group setting?	Yes	No

Participation Compensation:	

~

Subjects will not be paid for participation in this study.

### **Assent Process: N/A**

#### Benefits:

Potential benefits will be a relief of symptoms, avoidance of surgery, and return to full activity in the military setting.

#### **Risks:**

Procedural risks for an IMP needle insertion for intramuscular pressure testing may include pain, bleeding, and infection. There is a potential for no relief of CECS symptoms with either treatment intervention. Potential side effects of Botulinum toxin injections include possible pain, bleeding, infection, general muscle weakness, muscular atrophy, flu-like symptoms, breathing and swallowing difficulties and death. Potential side effects of fasciotomy include surgical site pain, bleeding, recurrence of symptoms, scarring, muscle weakness, nerve damage, hematoma, need for repeat operation, infection, reactions to anesthesia (e.g. anaphylaxis), blood clot, muscle wasting (atrophy), and death.

Costs: N/A

# **Safeguards for Protecting Information:**

The research consents will be stored in a locked cabinet in a locked room. Medical records will be annotated with ICD-10 code Z00.6 to reflect the subject's participation in a research study. All research data including patient demographics will be kept in an electronic database, which will be encrypted, double password protected and the access will be restricted. The research data will be coded and any links to identifiable data will be destroyed as soon as the Final Report Approval has been obtained from the IRB.

Data a	Data and Specimen Storage Plan						
How w	vill coded or identifiable data/specimens be !?						
Х	Paper data, including completed consent forms	The research data will be coded to mask the identity of the individual. They will be kept in a locked cabinet in a locked office.					
Х	Electronic data	All research data will be kept in an electronic database,					
Х	SSNs, Scrambled SSNs, or last four of SSNs	which will be encrypted, double password protected and the access will be restricted.					
Х	Long-term storage (following completion of the study and inactivation of IRB approval)	Once a Final Report has been approved by the IRB, all patient identifiers will be removed. The anonymized research data will not be utilized for further research activity beyond the protocol stipulations without additional IRB approval. The de-identified subject data, signed ICD and HIPAA documents, and the Regulatory Binder will be housed 3 years after the final report has been approved by the IRB.					

# Safeguards for Protecting Subjects Relative to Reasonably Expected Risks:

The subjects are not expected to experience any physical discomfort, psychological distress, or long term significant behavioral effects from their PHI being included in this study. The risk of invasion of private information is minimal as few identifiers will be used and will be protected, and any PHI will only be viewed by the investigators. Additionally, the data would not embarrass or disadvantage the participants if confidentiality were violated.

# Categories of subjects: None

## **Clinical Care:**

All subjects will receive standard care for any illness or disease found during the course of this study. At no time will this study preclude them from receiving any treatment for diseases related or unrelated to the study.

# Injury Compensation: N/A

Data Safety Monitoring	✓ N/A – none of the situations listed above apply
---------------------------	---

#### 5. ALTERNATIVES

### **Alternatives:**

Alternatives to participation in the study are continued conservative management to include rest, stretching, icing, and anti-inflammatory medications. Other options are to proceed with standard of care surgical fasciotomy or to do nothing.

### 6. DATA ANALYSIS

## **Data Analysis:**

Head-to-head comparison of patients undergoing or who have undergone standard of care surgical fasciotomy and investigational Botulinum toxin injections will be analyzed. Measures addressed will be pain severity, return to full activity, Lower Extremity Function index, and patient satisfaction over the course of pre-treatment, post-treatment, and 1, 3, 6 month follow-up visits.

A power analysis, shown below, was completed for this pilot study. Assuming equal sample sizes of groups, 2-tail alpha of .05, power=.8, and 67% of fasciotomy group will have no pain (i.e. pain < 3).4

- 1. 75% of injection group, no pain n=1008 total
- 2. 80% of injection group, no pain n=360 total
- 3. 85% of injection group, no pain n=176 total
- 4. 90% of injection group, no pain n=98 total
- 5. 95% of injection group, no pain n=60 total

As CECS is an infrequent diagnosis, this pilot study will have difficulty over the course of the year to obtain enough sample size for statistical significance. However, the hope is to obtain a promising trend and eventually expand the study to obtain significance pending initial results.

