## **Background and Review of Literature:**

The long term objective of this project is to validate botulinum toxin injections as a non-inferior treatment option for pain control and ability to return to full activity for adult military members suffering from lower extremity Chronic Exertional Compartment Syndrome (CECS), when compared to surgical fasciotomy. CECS is a debilitating disorder in which pressure in muscle compartments increases with exercise and resolves with rest. This causes pain, paresthesia, and inability to tolerate exercise. CECS mainly afflicts the lower extremities, below the knee, but upper extremity CECS has also been reported. CECS mainly affects young active adults. At risk groups include males, active duty military members, and athletes, both professional and recreational. 1,3,4,5

The current standard for definitive management and treatment of CECS is surgical fasciotomy. According to a 2016 systematic review, surgical intervention for CECS is successful in only 66% of those affected, with 13% of patients reporting complications from surgery, and 6% needing a repeat procedure. Definition of success varied across studies, but included patient satisfaction, lack of surgical revision, and full return to activity. Besides risks and complications, surgery also required a mean of 13 weeks to return to full activity when effective. A 2011 Cohort showed 81% overall patient satisfaction with the procedure, but noted best results from fasciotomy were young participants <23 years old, who underwent isolated anterior compartment release. Satisfaction was defined as being pain free or significantly improved on a 5 point pain scale, varying from pain free to worse. A smaller 2014 retrospective chart review of elite athletes with CECS showed fasciotomy was initially successful in 85% with a mean return to elite activity of 10.4 weeks. However, 30.8 % had a return of symptoms within the follow-up period.

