### 3. RESEARCH DESIGN AND METHODS

## **Research Design and Methods:**

The study will be a prospective cohort pilot study designed to compare Active Duty patients, 18 years of age or older, with CECS undergoing two different treatment interventions. The first arm will be patients receiving investigational botulinum toxin injections. The second arm will be patients who undergo the standard of care surgical fasciotomy. Both arms will be evaluated for pain relief with the universal pain scale and lower extremity functional index (LEFI) surveys at pre-treatment and again at one, three, and six months post-treatment. At the six month follow up, subjects will be asked the Satisfaction Survey (in-person, via Survey Monkey or Google Forms). Clinical data that will be analyzed for research purposes in both groups include age, sex, height, weight, body mass index, time to diagnosis, minutes of exercise prior to onset of symptoms, minutes of rest before relief of symptoms, LEFI and pain on the Universal Pain Assessment Tool.

In addition, we will be conducting a retrospective review from July 1, 2016 through June 30, 2017 of patients who have been diagnosed with CECS and have undergone surgical fasciotomy. They will be asked to recall their symptoms both before and six months after their surgery, in order to complete the LEFI and Universal Pain Assessment Tool (in-person, via Survey Monkey or Google Forms). They will also be asked if they were satisfied with their treatment. A HIPAA Waiver Request will be used to access medical records and contact these individuals, followed by each subject being verbally consented to participate in the study prior to completing the LEFI and universal pain scale surveys (in-person, via Survey Monkey or Google Forms). If the subjects refuse to be consented, then no data will be gathered from the subjects or their medical records.

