#### a. Interventions and Observations:

If CECS is diagnosed by intramuscular pressure (IMP) elevation, patients will be offered Botulinum toxin injection regimen into the affected compartment or referral to orthopedic surgeon for a possible surgical fasciotomy. Patients will be provided information regarding both Botulinum toxin injections and fasciotomy. Patients will be allowed to discuss fasciotomy with a surgeon prior to making a decision to participate in the study, if desired. Potential side effects of Botulinum toxin injection include possible bleeding, pain, infection, general muscle weakness, muscular atrophy, flu-like symptoms, breathing and swallowing difficulties and death. Potential side effects of fasciotomy include surgical site pain, bleeding, recurrence of symptoms, scarring, muscle weakness, nerve damage, hematoma, need for repeat operation, infection, reactions to anesthesia (e.g. anaphylaxis), blood clot, muscle wasting (atrophy), and death. These will be explained to participants during the consent discussion.

For those diagnosed with CECS and desire Botulinum toxin injections, they will receive 2 injections per affected compartment. Up to 50 units of Botulinum toxin will be injected into the proximal and distal portions of the compartment for a maximum total dose of 100 units. A solution of 100 units of Botulinum toxin per 2 mL of normal saline will be used for all injections. Standard sterile technique will be followed. Insertion in to the correct compartment will be accomplished using general landmarks. The compartment will be separated into thirds measuring from the tibial plateau to the head of the calcaneus. Injections will be given at approximately 1/3 the distance from the tibial plateau for the proximal injection and 2/3 the distance from the tibial plateau for the distal injection. If the lateral or deep posterior compartment is affected, a total of 50 units Botulinum toxin will be given, 25 units per injection. If the anterior or superficial posterior compartment is affected, a total of 100 units Botulinum toxin will be given, 50 units per injection. Of note, CECS mainly affects the anterior and lateral compartments and is rarely seen in the superficial posterior or deep posterior areas.

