### **Statistical Analysis:**

The primary measure to be analyzed will be comparing pre- and post-treatment pain for each of the two treatment regimens using the universal pain scale. Additionally, participants will be evaluated for return to duty, overall patient satisfaction, and the Lower Extremity Functional Index will be compared pre- and post-treatment. The study team will complete the statistical analysis.

Number of Subjects:				
	# Planned to Enroll	# Enrolled	# Planned to Complete Study	TOTAL

Number of Subjects at Scott AFB	15	0	15	15
---------------------------------	----	---	----	----

Number of Data Records Entered into the Study:					
	# Planned to Enroll	# Enrolled	# Planned to Complete Study	TOTAL	
Number of Subjects at Scott AFB	10	0	10	10	

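### Treatment follows patient choice, and recalled surgical controls are added, but the plan does not say how baseline pain, age or other collected data enter the injection-versus-fasciotomy comparison

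*Combined protocol and SAP*

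**What the plan says.** Research Design and Methods describes the design: "The study will be a prospective cohort pilot study designed to compare Active Duty patients" under two interventions. Under Interventions and Observations, once CECS is confirmed, "patients will be offered Botulinum toxin injection regimen into the affected compartment or referral to orthopedic surgeon for a possible surgical fasciotomy". The arms are then defined by preference: "For those diagnosed with CECS and desire Botulinum toxin injections, they will receive 2 injections per affected compartment", with parallel wording for fasciotomy. A retrospective series of fasciotomy patients (surgery July 2016 to June 2017, expected number 10) is added. They are asked to recall their pain and function before surgery and six months after it.

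Baseline information is listed: "Clinical data that will be analyzed for research purposes in both groups include age, sex, height, weight, body mass index, time to diagnosis", followed by exercise and rest times, LEFI and pain. No method is attached to the list.

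Data Analysis plans the between-group comparison: "Head-to-head comparison of patients undergoing or who have undergone standard of care surgical fasciotomy and investigational Botulinum toxin injections will be analyzed", on pain, activity, LEFI and satisfaction "over the course of pre-treatment, post-treatment, and 1, 3, 6 month follow-up visits". Statistical Analysis names as the primary measure "comparing pre- and post-treatment pain for each of the two treatment regimens using the universal pain scale", with LEFI also compared before and after treatment. Outcome Measures defines adequate pain reduction as a score below 3.

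None of these sections mentions a between-group model, covariate, stratification, matching, table of baseline balance or caveat about self-selection.

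**The concern.** When patients pick their treatment, the groups can differ at the outset in ways that also affect the outcome. The protocol's own background gives an example for surgery: one cohort "noted best results from fasciotomy were young participants <23 years old, who underwent isolated anterior compartment release". Age is collected but given no role in the comparison. Affected compartment is not on the list of variables to be analysed, although pressure testing of all four compartments of both legs establishes it.

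The retrospective controls add other differences. The protocol describes no offer of injection to them, their surgery falls largely before injection data collection begins in April 2017, their scores are recalled, and only those who consent contribute.

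The threshold of pain below 3 is a fixed level after treatment. A group that starts with worse pain will tend to have fewer patients below it, even if the treatments work equally well.

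The Data Analysis section makes expansion of the study depend on an encouraging trend in the initial results. A trend produced by who chose which treatment would feed directly into that decision.

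**Working it through.** **1. The plan's own between-group calculation.** The only between-group calculation shown is the power analysis: 67% of the fasciotomy group with pain below 3, two-sided alpha 0.05, power 0.80, equal groups. The pooled two-proportion formula is

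n per group = [1.96·√(2·p̄(1−p̄)) + 0.842·√(p1(1−p1) + p2(1−p2))]² / (p2−p1)².

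For 67% v 80%: p̄ = 0.735, and n = (1.2233 + 0.5196)² / 0.13² = 179.7, rounded up to 180, total 360. For injection rates of 75, 80, 85, 90 and 95% the totals are 1008, 360, 176, 98 and 60. All five match the plan. They are sizes for an unadjusted test of the share below 3, with no baseline variable. The target differences are 8, 13, 18, 23 and 28 percentage points.

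**2. What a baseline difference could do if the treatments were equal.** The documents give no SD, no correlation and no expected baseline gap, so these are assumptions:

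- post-treatment scores roughly normal, SD 2;
- slope of post-treatment on baseline pain 0.5 (range 0.3 to 0.7);
- surgery patients worse at baseline by 0.5 to 1.5 points;
- no treatment difference.

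Set the reference mean so that 67% score below 3: 3 − 2 × 0.440 = 2.12. The surgery group's mean then shifts by slope × gap.

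| Baseline gap | Slope | Shift in final pain | Share below 3, surgery group |
|---|---|---|---|
| 0.5 | 0.3 | 0.15 | 64% |
| 0.5 | 0.5 | 0.25 | 62% |
| 0.5 | 0.7 | 0.35 | 60% |
| 1.5 | 0.3 | 0.45 | 59% |
| 1.5 | 0.5 | 0.75 | 53% |
| 1.5 | 0.7 | 1.05 | 47% |

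For example, gap 1.5 and slope 0.5 give Φ((3 − 2.87)/2) = Φ(0.065) = 0.526. At slope 0.5, equal treatments would appear to differ by about 5 to 14 percentage points (67 − 62 to 67 − 53), so the larger gap exceeds the plan's two smallest targets (8 and 13). If injection patients were the worse group, the sign would reverse.

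**3. Change from baseline.** Under the same model, the difference in change is (1 − slope) × gap in the opposite direction. At slope 0.5 that is 0.25 to 0.75 points in favour of surgery. The plan does not say whether the groups will be contrasted on final score, change or share below 3, and here the answer depends on that choice.

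**4. A cruder check with one binary prognostic factor.** Spurious difference = (prevalence of good-prognosis patients in the injection group − prevalence in the surgery group) × (success rate with good prognosis − success rate with poor prognosis). With assumed inputs:

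- (0.60 − 0.40) × (0.75 − 0.60) = 3 points;
- (0.70 − 0.30) × (0.80 − 0.55) = 10 points;
- (0.80 − 0.20) × (0.81 − 0.50) = 19 points.

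**5. Precision.** The expected numbers are 15 prospective and 10 retrospective, with no split of the 15. In the most favourable pooled case (15 injected, 10 fasciotomy, SD 2), the 95% half-width for mean pain is 2.069 × 2 × √(1/15 + 1/10) = 1.7 points. For the share below 3 at 67% it is 1.96 × √(0.67 × 0.33 × (1/15 + 1/10)) = 38 percentage points. With 25 patients, about two covariates is the practical limit.

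**The case against.** A reader might infer that baseline data are not used at all. The text does not support that. The pre/post comparison by regimen uses pre-treatment pain and LEFI, pre-treatment is among the time points compared, and the other variables are to be analysed in both groups. What is missing is how any of this enters the contrast between groups.

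A reader might also infer that all patients chose between the two treatments, or that the head-to-head comparison is the plan's whole answer to its non-inferiority goal. Choice between the two describes only the prospective part. The second goal under Hypotheses, Research Questions, or Objectives is worded partly as a comparison with existing data and previous studies.

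Adjustment is not a cure. It corrects only for baseline pain that is accurately measured, and recalled scores are not that. Nor is the change-score result general: where groups differ stably before treatment, change scores can be unbiased and baseline adjustment biased (Lord's paradox). This stands, and is a reason to report both.

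Finally, this is a self-described pilot that expects to fall short of significance, and sampling error (half-width about 1.7 points) exceeds the illustrated bias. That lowers the severity. It does not remove the point, because confounding does not shrink as the study expands, and expansion depends on the trend seen here.

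**Conclusion.** The concern holds in a limited form. Prospective treatment is by patient choice, recalled surgical controls are added, and no section says how the between-group comparison is to be protected from baseline differences or that it should be read with caution. A difference in who receives each treatment may therefore be mistaken for a treatment effect.

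The size is unknown. With SD 2, slope 0.5 and a baseline gap of 0.5 to 1.5 points, equal treatments would differ by 0.25 to 0.75 points on final pain, and the surgery group's share below 3 would be about 62% to 53% instead of 67%. The gap, the slope, the SD and the direction are all assumptions. The documents do not show that such a gap will occur, nor that the sponsor will claim a causal effect. This is a should-fix point.

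**What to change.** In Data Analysis and Statistical Analysis, before outcome data are examined:

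- Pre-specify the between-group comparison as a linear model of 6-month pain on treatment, pre-treatment pain and age, with a 95% confidence interval. Analyse LEFI the same way with its own baseline.
- Report alongside it the unadjusted difference, the difference in change from baseline, and the share below 3 in each group.
- Tabulate the listed baseline variables and the affected compartment by group, where available.
- Show prospective and retrospective fasciotomy patients separately, because the latter have recalled baselines.
- State that the result is an adjusted, descriptive association that cannot by itself establish non-inferiority.

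The cost is mainly analysis wording and two degrees of freedom. Prospective pain, LEFI and age are already on the data list. Affected compartment comes from the diagnostic test and would need to be added to the list. For retrospective patients the plan specifies only recalled pain and LEFI and satisfaction, so age and the other variables would have to come from the medical record under the access already described. Residual confounding remains, and the text should say so.

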# Hypotheses, Research Questions, or Objectives:

In adult military patients with confirmed CECS by intramuscular pressure (IMP) needle measurements, botulinum toxin injections may be a non-inferior effective alternative to surgical fasciotomy in reduction of pain and ability to return to full activity. Therefore, the goals of this project are 1) To determine the long term efficacy of botulinum toxin injections in CECS. 2) Compared with current data and previous studies, is botulinum toxin injections non-inferior to current treatment regimens for overall pain control and return to full activity.

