# **Outcome Measures:**

For the prospective portion of the study, the primary outcome will be pain reduction from either a standard of care surgical fasciotomy or an investigational Botulinum toxin treatment regimen. Adequate pain reduction will be rated as less than 3 on the universal pain scale. Secondary outcomes will include return to full activity and patient satisfaction. Full activity is defined as being able to run 1.5 miles and complete work duties with either no pain or pain that can be ignored. To assess patient satisfaction, patients will be asked if they were or were not satisfied with their surgical fasciotomy or their Botulinum toxin injections during their 6 month follow-up visit.

For the retrospective portion of the study, the same measures will be addressed for subjects who have undergone a standard of care surgical fasciotomy, but only on a pre- and post-treatment basis.

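### Goal 2 asks a non-inferiority question, but the plan gives no margin or interval rule, its only power table is for superiority, and that table's control rate is not shown to be a pain <3 rate

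*Combined protocol and SAP*

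**What the plan says.** **Objective.** The Hypotheses section lists two goals. The second reads: "Compared with current data and previous studies, is botulinum toxin injections non-inferior to current treatment regimens for overall pain control", and it goes on to return to full activity. The hypothesis in the same section names the comparator: "botulinum toxin injections may be a non-inferior effective alternative to surgical fasciotomy in reduction of pain and ability to return to full activity". The Background section places the aim further off: "The long term objective of this project is to validate botulinum toxin injections as a non-inferior treatment option".

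**Analysis.** The Data Analysis section commits to a between-group comparison: "Head-to-head comparison of patients undergoing or who have undergone standard of care surgical fasciotomy and investigational Botulinum toxin injections will be analyzed". It lists measures and visits (1, 3 and 6 months) but selects no visit, estimate, interval or decision rule. The Statistical Analysis section defines the primary measure as "comparing pre- and post-treatment pain for each of the two treatment regimens using the universal pain scale". No section gives a margin.

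**Power.** The table rests on this statement: "Assuming equal sample sizes of groups, 2-tail alpha of .05, power=.8, and 67% of fasciotomy group will have no pain", where no pain is glossed as a score below 3 and reference mark 4 is attached. Total sizes are 1008, 360, 176, 98 and 60 for injection rates of 75, 80, 85, 90 and 95%. The text then concedes that significance will be hard to reach, and says "the hope is to obtain a promising trend and eventually expand the study to obtain significance pending initial results". Expected enrolment is 15 prospective and 10 retrospective patients, with no split by arm.

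**Control rate.** The Purpose and Background sections both give 66% for surgical success. The Background attributes it to a 2016 systematic review in which the definition of success varied and included satisfaction, absence of revision and full return to activity.

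**The concern.** A non-inferiority conclusion needs a margin and a rule for judging an interval for the between-arm difference against it. The plan has neither, for the fasciotomy patients it will study or for the published results that goal 2 also invokes. Pre/post change within each regimen does not estimate the difference between regimens. The only planning figures ask whether injection is better than fasciotomy, so they do not inform goal 2.

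At stake is how the result is read. Without a rule fixed in advance, there is no stated basis for saying whether a small or non-significant difference in about 25 patients supports goal 2. The same planning figures also rest on a control rate labelled as the trial's own pain threshold, and nothing in the documents shows that it was measured that way.

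**Working it through.** **1. Reproduce the power table.** The inputs are control 67%, injection 75–95%, two-sided 0.05, 80% power and equal groups (Data Analysis section). The pooled-variance formula per group is

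n = [1.96·√(2p̄(1−p̄)) + 0.8416·√(p₁(1−p₁) + p₂(1−p₂))]² / (p₂−p₁)²

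For 67% against 75%, p̄ = 0.71 and n = (1.2577 + 0.5380)² / 0.08² = 503.8. That rounds up to 504 per group, 1008 in total.

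| Injection rate | Stated total | Recomputed, 67% control | Recomputed, 66% control |
|---|---|---|---|
| 75% | 1008 | 1008 | 804 |
| 80% | 360 | 360 | 314 |
| 85% | 176 | 176 | 160 |
| 90% | 98 | 98 | 92 |
| 95% | 60 | 60 | 58 |

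All five rows match at 67%. Of the variants tried at 67% (continuity-corrected, one-sided, unpooled, arcsine), none reproduces the table. So 67% was the input used, the test is a two-sided test of a difference, and there is no margin and no equal-efficacy row.

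**2. What a non-inferiority calculation would look like.** The documents give no margin, so 10, 15 and 20 points are assumed. With one-sided 0.025, 80% power and equal groups,

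n per group = (1.96 + 0.8416)²·[p_c(1−p_c) + p_t(1−p_t)] / (margin + p_t − p_c)²

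- Both arms at 67%, 10-point margin: 7.849 × 0.4422 / 0.01 = 347.1, so 348 per group and 696 in total. For 15 and 20 points the totals are 310 and 174.
- Injection truly 75%, 10-point margin: 7.849 × 0.4086 / 0.18² = 99.0, so 99 per group and 198 in total. For 15 and 20 points the totals are 122 and 82.

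**3. What 25 patients would give.** The arm split is not stated, so two are assumed (injection/fasciotomy):

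- 15/10: every prospective patient is injected, as the Dates section might suggest.
- 8/17: 8 prospective patients are injected, and the other 7 join the 10 retrospective patients in having fasciotomy. The Research Design section does describe a prospective fasciotomy arm.

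Averaging the Newcombe 95% half-width over all binomial outcomes at 67% in both arms gives 32.8 points (15/10) and 33.7 points (8/17). The simpler Wald formula, 1.96·√(0.67·0.33·(1/15 + 1/10)), gives 37.6 points for 15/10.

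The same enumeration, with control at 67%, gives the chance that the lower Newcombe bound lies above minus the margin:

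| Split | True injection rate | 10 points | 15 points | 20 points |
|---|---|---|---|---|
| 15/10 | 67% | 9% | 18% | 22% |
| 15/10 | 75% | 19% | 34% | 37% |
| 15/10 | 85% | 42% | 61% | 62% |
| 15/10 | 95% | 73% | 89% | 89% |
| 8/17 | 67% | 6% | 11% | 17% |
| 8/17 | 95% | 52% | 66% | 78% |

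**4. The control input.** The power table says 67%, calls it a pain <3 rate and cites reference 4, which the bibliography shows is a 2016 systematic review of surgical management. The Background gives 66% from a 2016 systematic review with mixed success definitions. The Background sentence carries no reference number in the text available here, so treating the two as one source is an inference, though a natural one. The one-point gap moves the first row by 204 patients (1008 − 804, about 20%) and the last by 2 (60 − 58).

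**The case against.** The strongest reply is that the plan is candid. It calls itself a pilot, says its purpose is feasibility, concedes that significance is unlikely, looks to a later expansion and makes non-inferiority the project's long-term objective. It nowhere promises a formal non-inferiority test. The table does not drive enrolment either: 15 and 10 stand apart from it, so correcting it changes no sample size. All of that stands, and it limits the point to what may be concluded. It does not answer the point, because the caveat speaks of failing to reach significance, while goal 2 asks a question that a significance test for superiority does not address.

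Four stronger readings are tempting, and the documents do not support them.

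- **The power table is miscalculated.** It is not; every row reproduces.
- **Twenty-five patients make non-inferiority hopeless.** That follows only if equal efficacy is assumed. At the plan's own injection rates of 75–95%, the chance of clearing the assumed margins under 15/10 runs from 19% to 89%. Size alone does not rule out a pre-specified margin.
- **The 67% is wrong, or reference 4 contains no pain <3 rate.** Reference 4 cannot be seen here. The gap could be rounding or another figure from the same source, and the Background's list of definitions may not be complete. What can be said is that the documents do not support the label.
- **The sponsor intends to present a non-significant result as non-inferiority.** Nothing in the plan says so. The risk comes from the absence of a rule.

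**Conclusion.** The point stands as a mismatch between a stated goal and the plan for answering it. Followed as written, the plan cannot support a formal non-inferiority conclusion, because it has no margin, no interval rule and no defined between-arm estimate, and its planning figures address superiority. This does not invalidate the pilot, whose data can support a between-arm estimate. It should be fixed before analysis.

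The absence of a margin and rule, and the superiority form of the table, are read directly from the documents and need no assumption. The precision and probability figures are illustrations: they depend on assumed margins, assumed splits and a 67% control rate. The 67%/66% difference is a secondary matter of source and definition. Which figure is right cannot be told from the documents.

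**What to change.** 1. **Hypotheses and Statistical Analysis sections:** specify the between-arm estimate. This is the injection-minus-fasciotomy difference in the proportion with pain <3, and in return to full activity where collected, with a 95% CI by a small-sample method such as Newcombe. Use 6 months, the only post-treatment point the retrospective patients report (Research Design section).
2. **Goal 2:** reword it for this pilot as estimation, and keep non-inferiority as the long-term aim in the Background. If the sponsor prefers to keep a non-inferiority conclusion, it must instead pre-specify a margin and a CI rule. Estimation is the simpler choice with about 25 non-randomised patients, some reporting from recall.
3. **Data Analysis and Sample Size sections:** label the table as superiority planning that does not address goal 2. State the sponsor's expected arm split and the precision it implies; the 33 to 34 points above show the order of magnitude and are not figures to copy in. If all 15 prospective patients receive injection, no comparison within the prospective patients is possible, and the plan should say so.
4. **Control rate:** check 67% against reference 4 and state which outcome definition it reflects. If 66% is the intended input, restate the table as 804/314/160/92/58.

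The cost is a more modest stated aim and one visit fixed in advance. No extra patients, visits or procedures are required.
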